**Duration of Treatment for Individual Patients and Duration of Study:**

Patients enrolled under Phase 1 and Phase 2a portions of this study may continue to receive cerdulatinib in the absence of disease progression or intolerable toxicity or until they meet any other withdrawal criteria (Section 4.4). The total duration of the study (Phase 1 and Phase 2a) is expected to be ~6 years.

**Reference Therapy, Dosage, and Mode of Administration:** None.

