7. STATISTICAL METHODS

7.1 Data Analysis General Considerations

Where applicable, descriptive statistics will be provided. For continuous variables, n, mean, standard deviation (SD), median, minimum, and maximum will be presented. For discrete variables, the frequency and percentage will be presented. For time to event variables, unless specified otherwise, the Kaplan-Meier (KM) estimate and corresponding two-sided 95% confidence intervals (CIs) will be presented for the median and quartiles and, as necessary, for the event-free rates at the selected time points.

All calculations and analyses will be performed using SAS version 9.4 or higher.

Unless specified otherwise, the Phase 1 portion will be summarized by the initial assigned dose level and the Phase 2a portion will be presented by cancer type. Summaries and analyses will be done for Phase 1 and Phase 2a separately. There will be no pooling of Phase 1 and Phase 2a data. For the subjects enrolled in Phase 1 but continued in Phase 2a, only baseline information (baseline demography, disease characteristics, and prior anti-cancer therapies) from Phase 1 database will be used for corresponding Phase 2a summary tables, all other data will remain separate in Phase 1 and Phase 2a summary tables unless specified otherwise.

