7.9. Safety Analysis

All safety analyses will be performed in the safety analysis population.

Safety will be primarily assessed on the basis of adverse events (AE) rates. Clinical laboratory data, ECG findings, physical examinations, and vital signs will also be used for determining safety. Descriptive statistics will be used to summarize the safety data. The Phase 1 portion will be summarized by the initial assigned dose level and the Phase 2a portion will be presented by cancer type.

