7.9.1 Treatment Exposure and Compliance

Extent of exposure to study drugs will be summarized descriptively as the number of cycles started, duration of treatment, duration of treatment without full-day dose interruption (defined as full-day with 0 mg dose actually taken), cumulative total dose per subject, actual dose intensity and relative dose intensity.

The number and percentage of subjects with dose reductions, dose interruptions, dose interruptions ≥ 3 days that are not immediately followed by the end of treatment due to disease progression, and drug discontinuation will be tabulated, and the primary reason for dose modifications will be summarized.

The actual dose intensity (mg/day) is defined as the actual cumulative dose (mg) taken based on the total dose per day divided by treatment duration. The relative dose intensity (RDI) is defined as the ratio of actual dose intensity to the planned dose intensity (i.e. the initial assigned dose level in mg/day) in percentage.

Time to first occurrence of dose reduction/interruption due to an AE will be summarized descriptively. In addition, time to treatment failure, defined as time from start of study treatment to discontinuation of study treatment due to any reason, will be summarized.

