7.8.1. Adverse Events

Summary tables and listings will be provided for all reported treatment emergent adverse events (TEAEs), defined as AEs that start on or after the first day of any study drug that is administered and within 30 days of the last administration of any study drug. Missing and partially missing AE start dates will be imputed according to the specification described in Appendix A. The reported AE will be coded using MedDRA (version 16.1 for Phase 1; version 21.1 or higher for Phase 2a). AEs severity grading scales in Phase 1 are based on the NCI CTCAE version 4.03. For AEs in Phase 2a, AE severity grades are mixture of grading scales of the NCI-CTCAE version 4.03 and the NCI CTCAE version 5. No imputation of AE grades will be performed. AE with missing CTCAE grade will only be summarized in the all-grade column.

The causal relationship between the occurrence of an AE and each treatment will be assessed by the investigator. For summary of related AEs, causality assessment by the investigator per eCRF will be mapped based on Table 2. If the assessment of the relationship of an AE to study treatment is missing, the AE is assumed to be related to the study treatment in the table summary. No imputation will be done in the AE listings.

Table 2. Causality Mapping of AEs

Relationship to Study Drug per Investigator	Summary of AEs
Unrelated	Not related
Unlikely	Not related
Possible	Related
Probable	Related

TEAEs will be summarized based on the number and percentage of subjects experiencing AEs. When summarizing TEAEs by MedDRA system organ class (SOC) and preferred term (PT), a subject reporting the same AE more than once will be counted only once when calculating the incidence 1) within a given SOC, and 2) within a given SOC-PT combination. Similarly, a same AE will be counted only once within a PT when summarizing by PT only. In both situations, the maximum CTCAE toxicity grade and the strongest causal relationship to the study drug for such events will be used.

Tabular summaries of the following will be provided:

- TEAEs by PT
- TEAEs by SOC, PT
- TEAEs by SOC, PT, and maximum severity grade
- Grade 3 or higher TEAEs by PT
- Grade 3 or higher TEAEs by SOC, PT
- Grade 3 or higher TEAEs by SOC, PT and maximum severity grade
- Cerdulatinib-related TEAEs by PT
- Cerdulatinib-related TEAEs by SOC, PT
- Cerdulatinib-related TEAEs by SOC, PT, and maximum severity grade
- Rituximab-related TEAEs by PT (Cohort 2 only)

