- Rituximab-related TEAEs by SOC, PT (Cohort 2 only)
- Rituximab-related TEAEs by SOC, PT, and maximum severity grade (Cohort 2 only)
- Serious TEAEs by PT
- Serious TEAEs by SOC, PT
- TEAEs leading to cerdulatinib discontinuation by PT
- TEAEs leading to cerdulatinib discontinuation by SOC, PT
- TEAEs leading to cerdulatinib reduction by PT
- TEAEs leading to cerdulatinib reduction by SOC, PT
- Fatal TEAEs by PT
- Fatal TEAEs by SOC, PT.

TEAEs leading to rituximab dose modifications and discontinuations will be listed only.

Summaries (all-grade and grade 3 or above) will be provided for cytopenia category by combining following preferred terms in the AE dataset:

- Neutropenia: neutropenia, neutrophil count decreased, febrile neutropenia
- Thrombocytopenia: thrombocytopenia, platelet count decreased
- Anaemia: anaemia.
- Leukopenia: leukopenia, white blood cell count decreased
- Lymphopenia: lymphopenia, lymphocyte count decreased

For the following categories of TEAEs of special interest, the time to the first onset of the event will be analyzed (e.g. median/mean and min/max).

- All-grade gastrointestinal disorders of special interest
- Grade 3 or higher gastrointestinal disorders of special interest
- All-grade infections of special interest (lower respiratory bacterial infections)
- Grade 3 or higher infections of special interest (lower respiratory bacterial infections)

The relationship between all-grade infections of interest and concomitant compliance use of antimicrobial prophylaxis will be explored. In addition, gastrointestinal disorders and infections of special interest may be analyzed for certain population subgroups as appropriate.

In addition, selected safety summaries will be repeated for the subset of phase 2a subjects with 30 mg BID as starting cerdulatinib dose.

A summary of the number of deaths and the primary cause of death, classified by deaths within 30 days of last dose of study drug and deaths beyond 30 days after the last dose, will be provided.

7.8.1.1. Dose limiting toxicity in Phase 1

The number and percentage of patients experiencing dose limiting toxicities as captured in the eCRF by the investigator during Phase 1 will be summarized by initial dose cohort.

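### The planned summaries of GI and infection events of special interest mix risk with time on treatment and cannot show whether risk is early or accumulating

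*SAP*

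**What the plan says.** SAP 7.8.1 (Adverse Events) names four special-interest groupings: gastrointestinal disorders, and infections such as "All-grade infections of special interest (lower respiratory bacterial infections", each for all grades and for Grade 3 or higher. For these, "the time to the first onset of the event will be analyzed (e.g. median/mean and min/max". It adds an exploration of infections against antimicrobial prophylaxis and optional subgroup analyses. It states no number and percentage for the groupings themselves. For cytopenias, by contrast, the same section lists the preferred terms to be combined and commits to all-grade and Grade 3 or higher summaries.

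Elsewhere in that section, "TEAEs will be summarized based on the number and percentage of subjects experiencing AEs". An event counts as treatment-emergent if it starts on or after the first dose and "within 30 days of the last administration of any study drug". Under the protocol synopsis, patients "may continue to receive cerdulatinib in the absence of disease progression or intolerable toxicity". SAP 7.9 (Safety Analysis) says that "the Phase 2a portion will be presented by cancer type".

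Two related provisions matter. SAP 7.1 sets a default: "For time to event variables, unless specified otherwise, the Kaplan-Meier (KM) estimate and corresponding two-sided 95% confidence intervals (CIs) will be presented". SAP 7.9.1 (Treatment Exposure and Compliance) says: "Time to first occurrence of dose reduction/interruption due to an AE will be summarized descriptively". The same section tabulates cycles started, duration of treatment, dose intensity and time to treatment failure, but does not link them to adverse event incidence.

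**The concern.** An ordinary mean, minimum or maximum onset can be computed only from patients who had the event. Such a table leaves out the event-free patients and the time they were at risk. The crude percentages do keep every treated patient in the denominator, but they count events over a window whose length follows treatment. A cancer type that progresses early has less time to show events, and the events it does show must fall early.

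The tables will be read side by side by cancer type, and the protocol describes diseases with different courses: PTCL with inferior survival to B-cell NHL (1.6.3), and FL as an indolent lymphoma (1.6.4). Infection is also a harm of practical interest. Protocol 1.5 reports fatal related infections in Phase 1. Protocol 3.1.2.2.1 describes three of 12 Phase 2a patients who kept accumulating drug, two of whom had fatal infections. That section says causality could not be determined, and neither document shows that those infections belong to the SAP's lower respiratory bacterial category. Whether risk is early or builds up is still a question the safety report should be able to answer.

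**Working it through.** **Reading the onset sentence.** SAP 7.1 has two templates. For continuous variables it lists n, mean, SD, median, minimum and maximum. For time-to-event variables it lists Kaplan-Meier median, quartiles and 95% confidence intervals. The statistics named for onset match the first. Against that, they are introduced as examples, the Kaplan-Meier default applies unless otherwise specified, and only time to response (7.8.2.3) is expressly taken out of it. Events-only is therefore the likely reading, not the written one. The population and the censoring rule are not stated.

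**Plan's own figures.** The documents give no rate, onset time or exposure by cohort for these events, so there is nothing to reproduce. What follows is illustration on assumed inputs.

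**Fixed time at risk.** Assume a constant monthly hazard h and T months at risk. The proportion with the event is P = 1 − exp(−hT); the median onset among those with the event is −ln(1 − P/2)/h.

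| h | T (months) | P | Events-only median |
|---|---|---|---|
| 0.05 | 2 | 1 − exp(−0.10) = 9.5% | 1.0 month |
| 0.05 | 12 | 1 − exp(−0.60) = 45.1% | 5.1 months |
| 0.10 | 2 | 1 − exp(−0.20) = 18.1% | 1.0 month |
| 0.10 | 12 | 1 − exp(−1.20) = 69.9% | 4.3 months |

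**Variable treatment length.** Assume exponential treatment length with mean m months, plus 1 month for the 30-day window. The crude proportion is 1 − exp(−h)/(1 + hm). For h = 0.05 and m = 2 this is 1 − 0.9512/1.10 = 13.5%; for m = 12 it is 1 − 0.9512/1.60 = 40.5%. A simulation of 400,000 patients per setting agrees and supplies the medians:

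| h | Crude %, m = 2 / 12 | Events-only median, m = 2 / 12 (months) |
|---|---|---|
| 0.02 | 5.7 / 21.0 | 1.5 / 6.8 |
| 0.05 | 13.5 / 40.5 | 1.4 / 5.2 |
| 0.10 | 24.6 / 58.8 | 1.3 / 3.8 |

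The order can reverse: h = 0.10 with m = 2 gives 24.6%, below the 40.5% from half that hazard with m = 12.

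**Where the problem is small.** If all the risk falls in month 1 (30% in total), the crude percentage is 30% and the events-only median about 0.45 months at every duration. In that case a single person-time rate is the misleading measure: it falls from 0.135 to 0.032 per patient-month as m goes from 2 to 12, at identical risk. Crude percentages also carry real risk: with m = 6 in both groups, h = 0.05 and 0.10 give 26.8% and 43.4%.

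**What fixed-time measures do.** At h = 0.05 the person-time rate stays at 0.050 for every m. Kaplan-Meier, treating the end of the window as censoring, gives 13.9% at 3 months for every m. Aalen-Johansen with the end of the window as a competing event estimates something different: the probability of having the event by time t, allowing for stopping. For t > 1 and k = h + 1/m it is 1 − exp(−h) + h·exp(−h)·[1 − exp(−k(t − 1))]/k. With h = 0.05 this gives 10.6% (m = 2) and 13.2% (m = 12) at 3 months, and 13.5% and 32.3% at 12 months. It puts cancer types on one time axis and shows when events accrue. It does not remove treatment length from the later figures.

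**The case against.** The best defence is that this is a descriptive study with cohorts of about 20 to 50 and no formal safety analyses planned (Protocol 11.1.6). Percentages by system organ class and preferred term, all-grade and Grade 3 or higher, cover the components of the special-interest groupings, and serious and fatal events are tabulated as well. Exposure and time to treatment failure are in 7.9.1, so a reader can set one beside the other. The onset sentence gives examples only, and Kaplan-Meier is the default.

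Much of this stands. The component tables and exposure tables exist and give partial context. Events-only is an inference. But the grouped categories have no stated percentage, separate exposure tables do not let a reader recover risk by time, and the absence of a test does not stop tables by cancer type from being compared. If Kaplan-Meier is intended, 7.8.1 still has to state the population and censoring.

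A reader might infer that cohort differences will show treatment length instead of risk. The documents do not support that: crude percentages contain both, the balance depends on durations and hazard shapes that neither document gives, and for early-onset events the distortion is slight. Nor can the illustrative gaps be taken as the expected bias, since equal constant hazards were imposed.

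**Conclusion.** The concern holds in limited form. For the special-interest categories the SAP commits to an onset summary that is probably restricted to patients with the event, states no n (%) for the groupings, and plans neither cumulative incidence at fixed times nor any incidence that accounts for time at risk. Differences between cancer types will mix risk with treatment duration, and the summaries cannot separate early from accumulating risk. The size cannot be estimated from the documents. Under assumed equal constant hazards of 0.02 to 0.10 per month and mean treatment of 2 versus 12 months, crude percentages differ about 2.4- to 3.7-fold (58.8/24.6 and 21.0/5.7); for risk confined to month 1 they do not differ. The change is worth making before the tables are produced, but it affects interpretation of safety, not the primary endpoint.

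**What to change.** In SAP 7.8.1 (Adverse Events), for each special-interest category, all-grade and Grade 3 or higher, in all treated patients by cancer type:

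- Report n (%) for the grouped category.
- Report cumulative incidence at fixed times, for example 3, 6 and 12 months, by Aalen-Johansen. Treat as competing events death and the end of the adverse event window after treatment discontinuation for any reason, including toxicity. Censor patients still under observation at data cutoff. State that the estimate is the probability of the event allowing for stopping, so later time points still reflect treatment length.
- If person-time rates are shown, split them by period, for example the first 3 months versus later. They are the natural companion when risk while under observation is to be compared; a single overall rate misleads if risk is early.
- Label mean, median, minimum and maximum onset as *among patients with the event* and keep them as a supplement.

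Handle time to first AE-related dose reduction or interruption (7.9.1, Treatment Exposure and Compliance) the same way. This changes analysis only; no dosing or management rule is touched.

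The cost is additional table lines for four categories per cancer type, from event and dosing dates already collected. Estimates in cohorts of 20 to 50 will be imprecise, especially at 12 months, and should carry confidence intervals and numbers at risk.

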7.8.2. Laboratory Values

Summary tables will include descriptive statistics for the actual values and changes from baseline by scheduled time points in selected hematology, serum chemistry, and coagulation test results.

The incidence of potential Hy's law cases, identified as ALT/AST > 3 x ULN (upper limit of normal) and total bilirubin > 2 x ULN, will be summarized.

All parameters will be converted to consistent units according to the International System of Units before summarization.

All clinical laboratory results will be listed by subject and timing of collection.

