**Table 8: Guidelines for Dose Reductions for Cerdulatinib**

Toxicity	Occurrence	Action 
Hematologic Grade 3 or 4 febrile neutropenia Grade 4 neutropenia for $\geq 7$ days, or Grade 4 thrombocytopenia	1 st	Hold study drug. Once toxicity has resolved to Grade < 2 or baseline, may restart cerdulatinib at the next lower dose level.
	2 nd	Hold study drug. Once toxicity has resolved to Grade < 2 or baseline, may restart cerdulatinib at two dose levels below the starting dose.
	3 rd	Discontinue cerdulatinib
Gastrointestinal Grade 3 or 4 nausea, vomiting, or diarrhea if persistent despite optimal antiemetic or antidiarrheal therapy Grade 3 or greater increase in ALT/AST, total bilirubin	1 st	Hold study drug. Once toxicity has resolved to Grade < 2 or baseline, may restart cerdulatinib at the next lower dose level.
	2 nd	Hold study drug. Once toxicity has resolved to Grade < 2 or baseline, may restart cerdulatinib at two dose levels below the starting dose.
	3 rd	Discontinue cerdulatinib
Other Any other related Grade 3 or 4 non-laboratory toxicity Any other related Grade 3 or 4 laboratory toxicity considered clinically significant by the Investigator (e.g., symptomatic) (Do not dose reduce or hold study drug for asymptomatic amylase or lipase elevations  )	1 st	Hold study drug. Once toxicity has resolved to Grade < 2 or baseline, may restart cerdulatinib at the next lower dose level.
	2 nd	Hold study drug. Once toxicity has resolved to Grade < 2 or baseline, may restart cerdulatinib at two dose levels below the starting dose.
	3 rd	Discontinue cerdulatinib

AE = Adverse event; ALT = Alanine aminotransferase; AST = Aspartate aminotransferase

Note: Grading is NCI CTCAE v5.0.

 Do not dose reduce below 15 mg BID. At 15 mg BID, if any toxicity (Grade 3 or greater AE and/or any clinically significant AE) occurs, discontinue cerdulatinib (and rituximab for the combination cohort of cerdulatinib and rituximab) after completing the 30 Day Post-Last Treatment Visit in Section 7.3.2.2.

  $\geq$  Grade 3 asymptomatic elevations in amylase and lipase have been observed in this study without clinical pancreatitis.

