#### **10.2.4.4. Abnormal Laboratory Values**

Not every laboratory abnormality qualifies as an AE. A laboratory test result must be reported as an AE if it meets any of the following criteria:

- Is accompanied by clinical symptoms
- Results in a change in study treatment (e.g., dosage modification, treatment interruption, or treatment discontinuation)
- Results in a medical intervention (e.g., potassium supplementation for hypokalemia) or a change in concomitant therapy
- Is clinically significant in the investigator's in the investigator's judgment
  - Note: For oncology trials, certain abnormal values may not qualify as AEs.

It is the investigator's responsibility to review all laboratory findings. Medical and scientific judgment should be exercised in deciding whether an isolated laboratory abnormality should be classified as an AE.

If a clinically significant laboratory abnormality is a sign of a disease or syndrome (e.g., alkaline phosphatase and bilirubin  $5 \times$  ULN associated with cholestasis), only the diagnosis (i.e., cholestasis) should be recorded on the Adverse Event eCRF.

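### Apart from potential Hy's law cases, the SAP counts Grade 3-4 laboratory abnormalities only when they are reported as AEs or Phase 1 DLTs, so asymptomatic amylase/lipase rises and lesser or shorter cytopenias may go uncounted

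*SAP*

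**What the plan says.** **SAP 7.8.2 Laboratory Values.** The main output is described as follows: "Summary tables will include descriptive statistics for the actual values and changes from baseline by scheduled time points in selected hematology, serum chemistry". Coagulation tests are treated in the same way. SAP 7.1 defines the statistics: "For continuous variables, n, mean, standard deviation (SD), median, minimum, and maximum will be presented". One incidence is taken from laboratory values, that of potential Hy's law cases; the text reads "identified as ALT/AST > 3 x ULN (upper limit of normal) and total bilirubin > 2 x ULN, will be summarized". Finally, "All clinical laboratory results will be listed by subject and timing of collection".

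**SAP 7.8.1 Adverse Events.** "Summaries (all-grade and grade 3 or above) will be provided for cytopenia category by combining following preferred terms in the AE dataset". There are five such categories: neutropenia, thrombocytopenia, anaemia, leukopenia and lymphopenia. The section also plans tables of Grade 3 or higher TEAEs, and a Phase 1 count of DLTs as captured by the investigator.

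**Protocol 10.2.4.4.** "Not every laboratory abnormality qualifies as an AE". Reporting is required if the result comes with symptoms, changes study treatment, leads to an intervention or a change in concomitant therapy, or is clinically significant in the investigator's judgement.

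**Protocol Table 8.** Sites are told not to reduce or hold for asymptomatic amylase or lipase elevations. A footnote, in words that follow a greater-than-or-equal sign, says "Grade 3 asymptomatic elevations in amylase and lipase have been observed in this study without clinical pancreatitis".

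**The concern.** The AE dataset holds laboratory abnormalities that passed a reporting filter, and for some of them the filter is largely one investigator's opinion. A rate from that dataset mixes how often the abnormality occurred with how often someone chose to report it. The laboratory tables, which are free of this filter, do not count patients.

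The drug's history makes this relevant. Pancreatitis was a DLT at 45 mg BID (protocol 1.5). A Grade 3 chemical pancreatitis was among the events that preceded the lower starting dose in Amendment 5 (protocol 3.1.2.2.1). Protocol 5.2.1.2 and 7.5.2.1 ask for monitoring of leukocyte and cell counts. Changes in hematology and chemistry are a secondary endpoint in both phases. A report built to this plan could understate biochemical pancreatic toxicity and cytopenia, and differences between cohorts could partly reflect reporting habits.

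**Working it through.** The plan states no figure to reproduce. The check sets the planned outputs against the reporting rules.

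**1. Which outputs count patients, and from what source**

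| Output | Source | Counts patients by grade or threshold? |
|---|---|---|
| Grade 3+ TEAE tables | AE dataset | Yes |
| Cytopenia categories | AE dataset | Yes |
| Phase 1 DLT table | Investigator-captured DLTs | Yes, DLT criteria only |
| Potential Hy's law | Laboratory values | Yes, one combined criterion |
| Descriptive statistics by visit | Laboratory values, scheduled, selected tests | No |
| Listing | All laboratory values | No |

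Only the Hy's law row both uses laboratory values and counts patients. By contrast, SAP 7.8.4 tabulates patients by maximum QTcF and by maximum QTcF increase.

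**2. How each abnormality reaches the AE dataset**

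- *Grade 4 thrombocytopenia, Grade 4 neutropenia of at least 7 days, febrile neutropenia, Grade 3+ ALT/AST or bilirubin:* Table 8 directs a hold. A treatment change makes the result a required AE, so these should be counted.
- *Grade 3 neutropenia, shorter Grade 4 neutropenia, Grade 3 thrombocytopenia:* Table 8 does not name them. They fall under its residual laboratory row, which depends on the investigator finding them clinically significant. Without symptoms, treatment change or intervention, reporting rests on judgement.
- *Asymptomatic Grade 3+ amylase or lipase:* the symptom route is closed by definition and the treatment-change route by Table 8. An intervention or judgement remains.

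**3. Whether the by-visit minimum and maximum fill the gap**

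A lipase maximum above the Grade 3 limit at a visit shows that at least one patient crossed it. It does not show how many did, or whether the same patient crossed at the next visit. Results from unscheduled draws are outside these tables. Protocol 7.1.9.1, for example, requires repeat liver tests within 72 hours of a Grade 3+ ALT/AST rise, and a peak on the repeat would not appear.

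**4. Baseline**

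CLL patients may enter with ANC 750/µL and platelets 30,000/µL. Leukemic PTCL and hepatosplenic T-cell lymphoma have no lower limit if the cytopenia is due to disease (protocol 4.1.2). Separating entry cytopenia from on-treatment worsening needs a shift table.

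**5. Data availability**

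Protocol Table 2 records that routine chemistry gained amylase and lipase at Amendment 5 (14 October 2016), and that Phase 1 was closed to enrollment when Amendment 4 (6 April 2016) was implemented. The first 12 Phase 2a patients, at 35 mg BID, were dosed before Amendment 5. Routine amylase/lipase results therefore cannot be assumed for Phase 1 or the earliest Phase 2a patients. Hematology and liver tests do not have this limitation.

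**6. Illustration (assumed count)**

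Take 40 patients, the lower figure for an expanded cohort, and assume 6 have an asymptomatic Grade 3+ lipase rise. Exact (Clopper-Pearson) 95% limits for x of n are the 2.5% quantile of Beta(x, n − x + 1) and the 97.5% quantile of Beta(x + 1, n − x).

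- Laboratory-based: 6/40 = 15.0%, limits from Beta(6, 35) and Beta(7, 34), 5.7% to 29.8%.
- AE-based, none reported: 0/40, upper limit 1 − 0.025^(1/40) = 8.8%.

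Any AE count from 0 to 6 is possible under the same reporting rules.

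**The case against.** The strongest reply is that much laboratory toxicity is already counted. Events reported as AEs enter the Grade 3+ TEAE and cytopenia tables, and protocol Table 4 shows this happening in Phase 1, with neutrophil count decreased, LDH increased and AST increased. The most severe cytopenias and the liver values trigger a hold and so become required AEs. The pancreatitis cases were caught by existing reporting. All results are listed, and the listing is not limited to scheduled draws. Protocol 11.1.6 asks only for summaries and listings by time point, so the SAP does not contradict it.

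All of this stands, and it rules out two stronger readings. A reader might infer that laboratory data are summarised only as means. SAP 7.1 also gives SD, median, minimum and maximum, and a Hy's law incidence is planned. A reader might also infer that Grade 3-4 laboratory toxicity appears in no incidence table. It does appear when reported as an AE or a Phase 1 DLT.

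What the reply does not meet is the remainder: values that no rule forces into the AE dataset. A listing keeps them but gives no rate, and a visit extreme does not say how many patients had one.

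**Conclusion.** The point holds as an omission, not as an inconsistency between protocol and SAP. Apart from potential Hy's law cases, no incidence or shift table comes from graded laboratory values. The exposure is greatest for asymptomatic Grade 3+ amylase/lipase rises. It extends to cytopenias that are lesser or shorter than the Table 8 triggers and change no treatment, and to peaks seen only at unscheduled draws.

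The size of any under-count is unknown. The documents say the amylase/lipase elevations occurred but not how often, and the 6/40 example is an assumption, not an estimate. The conclusion assumes that some such values were not reported as AEs. If investigators reported every one, the AE rates would be complete apart from the missing shift information. The change is worth making because it is cheap and removes the dependence on reporting habits.

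**What to change.** In SAP 7.8.2 add, by cohort for Phase 2a, tables of worst post-baseline CTCAE grade and of shift from baseline to worst grade. Cover neutrophils, platelets, hemoglobin, lymphocytes, WBC, ALT, AST, bilirubin, amylase and lipase. Use scheduled and unscheduled results through 30 days after last dose, which matches the TEAE window. Name one CTCAE version for all laboratory grading, since the SAP acknowledges that Phase 2a AE grades mix versions 4.03 and 5.0. Present these tables beside the AE-based cytopenia rates.

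For amylase and lipase, use patients with a post-baseline value as the denominator and show that number. For Phase 1, give the hematology and liver tables by initial dose, and amylase/lipase only where data exist.

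The cost is SAP wording and modest programming, with no new patient procedures. Grading tests against normal limits needs the local laboratory ranges in the database. The Hy's law count already needs them for ALT, AST and bilirubin; their availability for amylase and lipase is an assumption to confirm. The downside is that reported laboratory toxicity rates may be less favourable.
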